5.2.3. Analyses for Categorical Endpoints

NA.

5.2.4. Analyses for Time-to-Event Endpoints

NA.

5.3. Methods to Manage Missing Data

The primary analysis will use the primary estimand binary endpoint set. This dataset by definition has no missing data since all missing values will have been set to a failure. Summaries will use the Observed Efficacy Set and will report results on an observed case (OC) basis. For continuous endpoint data, each landmark analysis (eg, Cross sectional analysis by week) missing data will be imputed using a control based imputation method. PROC MI will first be called at the visit and a control based method (implemented with the MNAR (Missing Not At Random)--option) will impute missing placebo observations under the assumption data are missing at random (MAR) and impute missing treatment observations assuming they are similar to corresponding placebo patients. Imputation will use the full conditional specification (FCS) method, the imputed data for the placebo arm will be combined for the analysis.

Summaries of continuous data will use the observed data only and no additional considerations are needed.

6. ANALYSES AND SUMMARIES

Analysis will be done pairwise between each of the PF-06826647 treated groups and the placebo group. An analysis with point estimates of the difference, the associated 90% confidence intervals and p-values will also be reported.

A summary of analyses for clinical efficacy endpoints is provided in [Appendix 1](#). Visit windows to be used for all efficacy analyses and some relevant safety analyses are detailed in [Appendix 2.1](#).

6.1. Primary Endpoint(s)

6.1.1. Proportion of Participants Achieving PASI90 at Week 16

6.1.1.1. Main Analysis

- Estimand strategy: Primary Estimand ([Section 2.1.1](#)) use a composite endpoint strategy. This estimand is intended to provide an estimate of the treatment effect in the absence of prohibited medication use in a population that may or may not be fully compliant with the treatment.
- Analysis set: mITT ([Section 4.1](#)) using data prepared in the description of the Primary Estimand Categorical Endpoint Set.
- Analysis methodology: Risk differences will be analyzed using the method of (Chan and Zhang 1999)² in PROC BINOMIAL.

- Intercurrent events and missing data: These have been accounted for in the preparation of the Primary Estimand Categorical Endpoint Set ([Section 4.4](#)). This prepared data set has no missing values.
- Proportions, risk differences and 90% confidence intervals will be presented.

6.1.1.2. Sensitivity/Supplementary Analyses

- Estimand strategy: Primarily this estimand is intended to provide an estimate of the treatment effect in the population level assuming missing data are either MCAS (Missing Completely at Random) or MAR (Missing at Random). Applicable statistics will be calculated at Week 16.
- Population: mITT.
- Analysis methodology: GLMM and descriptive statistics.
- Missing Data: Observed Data.

6.2. Secondary Endpoint(s)

6.2.1. Proportion of Participants Achieving PASI75

6.2.1.1. Main Analysis

- Estimand strategy: Primary Estimand ([Section 2.1.1](#)) use a composite endpoint strategy. This estimand is intended to provide an estimate of the treatment effect in the absence of prohibited medication use in a population that may or may not be fully compliant with the treatment. Applicable statistics will be calculated at time points specified in the SoA.
- Analysis set: mITT ([Section 4.1](#)) using data prepared in the description of the Primary Estimand Categorical Endpoint Set.
- Analysis methodology: Risk differences will be analyzed using the method of (Chan and Zhang 1999)² in PROC BINOMIAL.
- Intercurrent events and missing data: These have been accounted for in the preparation of the Primary Estimand Categorical Endpoint Set ([Section 4.4](#)). This prepared data set has no missing values.
- Proportions, risk differences and 90% confidence intervals will be presented.

6.2.1.2. Sensitivity/Supplementary Analysis

- Estimand strategy: Primarily this estimand is intended to provide an estimate of the treatment effect in the population level assuming missing data are either MCAS (Missing Completely at Random) or MAR (Missing at Random). Applicable statistics will be calculated at time points specified in the SoA.

- Population: mITT.
- Analysis methodology: GLMM and descriptive statistics.
- Missing Data: Observed Data.

6.2.2. Proportion of Participants with PGA 0/1, PGA 0/1 and ≥ 2 Points Improvements

6.2.2.1. Main Analysis

- Estimand strategy: Primary Estimand ([Section 2.1.1](#)) use a composite endpoint strategy. This estimand is intended to provide an estimate of the treatment effect in the absence of prohibited medication use in a population that may or may not be fully compliant with the treatment.
- Analysis set: mITT ([Section 4.1](#)) using data prepared in the description of the Primary Estimand Categorical Endpoint Set.
- Analysis methodology: Risk differences will be analyzed using the method of (Chan and Zhang 1999)² in PROC BINOMIAL.
- Intercurrent events and missing data: These have been accounted for in the preparation of the Primary Estimand Categorical Endpoint Set ([Section 4.4](#)). This prepared data set has no missing values.
- Proportions, risk differences and 90% confidence intervals will be presented.

6.2.2.2. Sensitivity/Supplementary Analysis

- Estimand strategy: Primarily this estimand is intended to provide an estimate of the treatment effect in the population level assuming missing data are either MCAS (Missing Completely at Random) or MAR (Missing at Random). Applicable statistics will be calculated at time points specified in the SoA.
- Population: mITT.
- Analysis methodology: GLMM and descriptive statistics.
- Missing Data: Observed Data.

6.2.3. Change and Percent Change From Baseline in PASI Score at Week 16

6.2.3.1. Main analysis

- Estimand strategy: Secondary Estimand ([Section 2.1.2](#)) use a composite endpoint strategy. This estimand is intended to provide an estimate of the treatment effect in the absence of prohibited medication use in a population that may or may not be fully compliant with the treatment.

- Analysis set: mITT (Section 4.1) using data prepared in the description of the Secondary Estimand Continuous Endpoint Set.
- Analysis methodology: ANCOVA model with treatments arms and baseline score as dependent variable.
- Intercurrent events and missing data: These have been accounted for in the estimand (Section 2.1.2) and missing data will be imputed using a contro based imputation method (Section 5.3).
- Mean difference of change/percent change from baseline PASI score and 90% confidence intervals will be presented.

6.2.3.2. Sensitivity/Supplementary Analysis

- Estimand strategy: Primarily this estimand is intended to provide an estimate of the treatment effect in the population level assuming missing data are either MCAS (Missing Completely at Random) or MAR (Missing at Random). Applicable statistics will be calculated at time points specified in the SoA.
- Population: mITT.
- Analysis methodology: MMRM and descriptive statistics.
- Missing Data: Observed Data.

6.2.4. Secondary Endpoints: Continuous Data

Analyses of all continuous endpoints such as PASI, CCI PP-NRS, PSI, CCI etc for their percentage change or absolute change from baseline or absolute values:

- Estimand strategy: Primarily this estimand is intended to provide an estimate of the treatment effect in the population level assuming missing data are either MCAS (Missing Completely at Random) or MAR (Missing at Random). Applicable statistics will be calculated at time points specified in the SoA.
- Population: mITT.
- Analysis methodology: MMRM and descriptive statistics.
- Missing Data: Observed Data.

6.2.5. Secondary Endpoint: Binary Data

Analyses of all binary endpoints such as PASI 50, PASI 75, PASI 90, PASI 100, PGA (0/1), PGA (0/1 and ≥ 2), CCI PSI (≤ 8 and 0/1), CCI for their proportions of participants will be as follows:

CCI

6.2.5.1. Main Analysis

- Estimand strategy: Primary estimand ([Section 2.1.1](#)) use a composite endpoint strategy. This estimand is intended to provide an estimate of the treatment effect in the absence of prohibited medication use in a population that may or may not be fully compliant with the treatment.
- Analysis set: mITT ([Section 4.1](#)) using data prepared in the description of the Primary Estimand Categorical Endpoint Set.
- Analysis methodology: Risk differences will be analyzed using the method of (Chan and Zhang 1999)² in PROC BINOMIAL.
- Intercurrent events and missing data: These have been accounted for in the preparation of the Primary Estimand Categorical Endpoint Set ([Section 4.4](#)). This prepared data set has no missing values.
- Proportions, risk differences and 90% confidence intervals will be presented.

6.2.5.2. Sensitivity/Supplementary Analyses

- Estimand strategy: Primarily this estimand is intended to provide an estimate of the treatment effect in the population level assuming missing data are either MCAS (Missing Completely at Random) or MAR (Missing at Random). Applicable statistics will be calculated at time points specified in the SoA.
- Population: mITT.
- Analysis methodology: GLMM and descriptive statistics.
- Missing Data: Observed Data.

6.3. Clinical Laboratory Values, ECG

The following endpoints will be summarized using available data and not modeled.

Change from baseline in clinical laboratory values, Change from baseline in ECG parameters (hear rate, QT, QTc, PR and QRS intervals). Estimand strategy: No estimand is applicable. Summary statistics will be calculated at time points specified in the SoA.

- Population: Safety Analysis Set.
- Analysis methodology: Summary statistics.
- Missing Data: Observed Data.

CCI [REDACTED]

6.5. Skin Biopsy

NA.

6.6. Subset Analyses

No subset analyses are planned; however the impact of different baseline subgroups on the primary and secondary endpoints may be explored on adhoc basis, and will not be reported in Clinical Study Report.

6.7. Baseline and Other Summaries and Analyses

6.7.1. Baseline Summaries

Demographic and baseline characteristics will be summarized by randomized treatment group for all randomized and treated subjects. Continuous variables will be summarized using mean and standard deviation. Categorical variables will be summarized using relative frequency. Key demographic and baseline variables to be summarized include: age, gender, race, ethnicity, height, weight, body mass index, disease duration, baseline PASI score, baseline PGA, CCI [REDACTED] etc.

6.7.2. Study Conduct and Participant Disposition

Subjects' evaluation, disposition and discontinuation will be summarized according to CaPS.

6.7.3. Study Treatment Exposure

A summary of dosing compliance by treatment group will be provided.

The exposure to study drug will be summarized by the total number of days of dosing, mean/median number of days of exposure and number and percent of subjects in exposure duration categories.

6.7.4. Concomitant Medications and Nondrug Treatments

Prior drug and non-drug treatment, concomitant drug and non-drug treatment will be summarized according to CaPS.

CCI [REDACTED]

6.8. Safety Summaries and Analyses

The analysis population for safety is described in [Section 4.4](#). Safety and tolerability will be assessed by clinical review of all relevant parameters including adverse experiences (AEs) and laboratory tests. A complete list of laboratory parameters can be obtained in [Section 10.2](#) of the protocol.

All the tables, listings and graphs for adverse events, lab parameters and vital sign and ECG will follow Pfizer standards.

6.8.1. Adverse Events

The binary safety endpoints including the incidences of on-treatment AEs, withdrawals due to AEs and serious AEs will be analyzed using the exact test described in [Section 5.2.1](#). A 3-tier approach will be used to summarize AEs. Under this approach, AEs are classified into 1 of 3 tiers.

Tier-1 events: These are pre-specified events of clinical importance and are maintained in a list in the product's Safety Review Plan. There are no Tier 1 events for this study. Tier 1 displays will not be created.

Tier-2 events: These are events that are not tier-1 but are "common". A MedDRA Preferred Term (PT) is defined as a tier-2 event if there are at least 4 subjects with an event in any treatment group.

Tier-3 events: These are events that are neither tier-1 nor tier-2 events.

There will be no adjustment for multiple comparisons or stratification factors in the analyses unless specified. For tier-1 and tier-2 events, the proportion of AEs observed in each treatment groups will be presented along with the point estimates and associated 95% confidence intervals of the risk difference for each active treatment compared with placebo using the exact methods described in [Section 5.2.1](#). For tier-1 events p-values may be included in the presentations. AEs will be arranged in the output sorted in descending point estimate of the risk difference within system organ class. Footnotes in the outputs will include the methods used to derive any p-values and confidence intervals as per Pfizer standards.

It should be recognized that most studies are not designed to reliably demonstrate a causal relationship between the use of a pharmaceutical product and an adverse event or a group of adverse events. Except for select events in unique situations, studies do not employ formal adjudication procedures for the purpose of event classification. As such, safety analysis is generally considered as an exploratory analysis and its purpose is to generate hypotheses for further investigation. The 3-tier approach facilitates this exploratory analysis.

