2.3. Benefit/Risk Assessment

PF-06826647 is expected to offer therapeutic benefit in the treatment of psoriasis. More specifically, inhibition of IL-12 and IL-23 signaling mediated by TYK2 inhibitory activity may provide a new and improved therapeutic benefit due to potential achievement of disease control, improvement of signs and symptoms, as well as improvements in quality of life.

Overall, the safety profile observed during the Phase 1 program for PF-06826647 appears to be acceptable at dosages up to 1200 mg daily administered orally over 10 days. A longer dosing duration was explored in participants with moderate to severe psoriasis, who received the maximum PF-06826647 dose level of 400 mg and 100 mg daily for 28 days. No serious or severe AEs were reported in the Phase 1 study. There was one psoriasis participant in the 400 mg cohort who met the protocol pre-specified stopping criteria due to decreased level of lymphocytes, although this participant had borderline low lymphocytes at baseline. As with other immunomodulators, the risk of infection is a potential concern due to the immunosuppressive effects of PF-06826647.

In conclusion, the sponsor considers that the available information from the nonclinical and clinical data to date regarding PF-06826647 provide a favorable benefit-risk profile and supports its continued investigation as a potential treatment for plaque psoriasis.

More detailed information about the known and expected benefits and risks and reasonably expected adverse events (AEs) of PF-06826647 may be found in the investigator's brochure, which is the single reference safety document (SRSD) for this study.

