9.4.2. Safety Analyses

All safety analyses will be performed on the safety population.

Endpoint	Statistical Analysis Methods
Primary	
The safety data will be summarized in accordance with Pfizer Data Standards. All participants who receive IP (safety population) will be included in the safety analyses. All safety data will be summarized descriptively through appropriate data tabulations, descriptive statistics, categorical summaries, and graphical presentations. Safety endpoints for the study include:
 
 • Treatment-emergent AEs and SAEs. • Withdrawals from active treatment due to AEs. • Serious infections, defined as any infection (viral, bacterial, and fungal) requiring hospitalization or parenteral antimicrobials. • Safety laboratory tests (eg, hematology [including coagulation panel], chemistry and lipid profiles). • Vital signs. 
Change from baseline on laboratory data and vital signs will be additionally summarized. Participant listings will also be produced for these safety endpoints.

CCI	

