3.4. Safety Endpoints

Safety will be assessed by the spontaneous reporting of AEs, physical examinations, and clinical laboratory results in all subjects who receive at least one dose of the investigational product. Unscheduled safety assessments may be performed at any time during the study to assess any perceived safety concerns. Endpoints will be assessed as:

- Incidence of treatment emergent adverse events.
- Incidence of SAEs and AEs leading to discontinuation.
- Incidence of clinical abnormalities and change from baseline in selected clinical laboratory values, ECG measurements, and vital signs.

The safety endpoints will be defined in accordance with Clinical Data Interchange Standards Consortium (CDISC) and Pfizer Standards (CaPS).

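### The SAP drops the protocol's serious-infections endpoint and names no Tier 1 events, so infections appear only by single preferred term or inside total AEs and SAEs.

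*SAP*

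**What the plan says.** **Protocol.** Section 2.3 states that "the risk of infection is a potential concern due to the immunosuppressive effects of PF-06826647". Section 9.4.2 then lists as a safety endpoint "Serious infections, defined as any infection (viral, bacterial, and fungal) requiring hospitalization or parenteral antimicrobials". For safety endpoints in general it promises that "All safety data will be summarized descriptively through appropriate data tabulations, descriptive statistics, categorical summaries, and graphical presentations", together with participant listings. Section 8.2.6 arranges a swab and a blood sample for viral load whenever a herpetiform rash is suspected.

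**SAP.** Section 3.4 names treatment-emergent AEs, "Incidence of SAEs and AEs leading to discontinuation", and abnormalities or changes in laboratory, ECG and vital-sign values. Serious infections are missing there, from the secondary endpoints in 3.1.2 and from the AE analyses in 6.8.1. The version history records no decision to remove them.

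Section 6.8.1 sets up three tiers:

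- Tier 1: "There are no Tier 1 events for this study. Tier 1 displays will not be created".
- Tier 2: "A MedDRA Preferred Term (PT) is defined as a tier-2 event if there are at least 4 subjects with an event in any treatment group". These terms receive "associated 95% confidence intervals of the risk difference for each active treatment compared with placebo using the exact methods".
- Tier 3: everything else, with no comparison specified.

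The same section opens with an analysis of totals: "The binary safety endpoints including the incidences of on-treatment AEs, withdrawals due to AEs and serious AEs will be analyzed using the exact test".

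**The concern.** The protocol's endpoint is a group: any infection that meets a severity-of-treatment criterion, whatever its MedDRA term. The SAP's tier rule works on one term at a time. Pneumonia, cellulitis and urosepsis in three participants are three serious infections under the protocol, but three separate single-subject terms under the tiers. Tier 1 would have been the natural place to pre-specify the group, and it is empty.

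The SAE total does not replace the group, for two reasons. It mixes infections with every other serious event. It also need not contain all of them: under Protocol 10.3.2, inpatient hospitalisation makes an event serious, but parenteral antimicrobial treatment alone is not a listed criterion. An infection treated that way as an outpatient meets the 9.4.2 definition and may still not be recorded as an SAE.

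At stake is whether the trial reports a grouped figure by arm for an endpoint its protocol defines, on a risk its protocol names. If the grouping is made only after unblinding, the choice of terms is open to influence from the results.

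**Working it through.** **Inputs.** Protocol 9.2 gives 128 completers, 20% dropout and 2:1:1:2:2 allocation. SAP 6.8.1 gives the threshold of 4 subjects. The documents state no expected infection rate, so every rate and count in steps 3 to 6 is assumed.

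**1. Reproduce the arm sizes.** 128 / (1 - 0.20) = 160, as stated. 160 / 8 = 20 per allocation unit, so 40 each on placebo, 200 mg and 400 mg, and 20 each on 50 mg and 100 mg. This also matches.

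**2. The threshold as a rate.** 4/40 = 10%; 4/20 = 20%. A term must be twice as frequent in the 50 mg or 100 mg arm to reach Tier 2 on that arm's data.

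**3. Chance that one term reaches Tier 2.** For an arm of size n and true rate p, the chance is P(X >= 4) with X binomial(n, p). If the rate is equal in all five arms, the chance that at least one arm reaches 4 is 1 - (1 - P40)^3 x (1 - P20)^2.

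| True rate of the term | One arm of 40 | One arm of 20 | Any of five arms, equal rate |
|---|---|---|---|
| 2% | 0.8% | 0.1% | 2.6% |
| 5% | 13.8% | 1.6% | 38% |
| 10% | 57.7% | 13.3% | 94% |
| 20% | 97.2% | 58.9% | about 100% |

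Check at 5%: 1 - 0.862^3 x 0.984^2 = 0.38. A common infection term would therefore usually be compared with placebo, and a rare one would not.

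**4. Effect of splitting.** Take an assumed total infection rate of 20% in a 40-participant arm. As one group, it reaches 4 subjects with probability 97.2%. Spread evenly over five terms (20% / 5 = 4% each), a given term reaches 4 in that arm with probability 7.5%.

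**5. Two illustrations for infections of any seriousness.**

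- Eight of 40 participants on one dose have infections, against 2 of 40 on placebo. As a group the risk difference is 20% - 5% = 15 points, with an exact unconditional 95% interval of about 0.5 to 31. If the eight fall under terms as 3 + 3 + 2, and no other arm reaches 4 on any of these terms, the tiers give no risk difference.
- One infection term occurs in 3 participants on each of the four doses and in none on placebo. That is 12/120 against 0/40 (two-sided Fisher p = 0.038), yet no arm reaches 4, so the term stays in Tier 3.

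In both cases the events still count in the overall AE total, but not as infections.

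**6. What the grouped serious-infection endpoint could deliver.** For 3/40 against 0/40 the risk difference is 7.5 points, with an exact 95% interval of about -1.5 to 20. With zero events, the one-sided 95% upper limit is 1 - 0.05^(1/n): 7.2% for n = 40 and 13.9% for n = 20. The grouped endpoint gives a defined estimate, but an imprecise one.

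**The case against.** A reader might infer that infections get no comparison with placebo at all. The documents do not support that. Hospitalised infections are SAEs under Protocol 10.3.2 and enter the exact test of total SAEs whatever their preferred term. Any infection term that reaches 4 subjects in any arm, placebo included and with non-serious events counted, is compared with placebo at every dose. For the same reason, the chance that four serious infections happen to share one term is not the chance of reaching Tier 2, because it leaves out non-serious events and the other arms. The first sentence of 6.8.1 is also an open list, so a further binary endpoint is not excluded.

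A reader might also take infection to be the protocol's leading safety concern. Section 2.3 calls it a potential concern. Sections 4.3 and 2.3 also discuss reticulocytes, erythropoietin inhibition and low lymphocytes.

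Other points against have weight. Protocol 9.4.2 promises descriptive summaries and listings, so no promised placebo comparison is broken. Section 8.2.6 is a specimen-collection procedure and defines no endpoint. An empty Tier 1 is not in itself an error. SAP 3.4.1 and 6.8.1 place the Tier 1 list in a Safety Review Plan, and 6.8 refers AE outputs to sponsor standards. Neither source is available here, so a grouped infection table may be produced under them.

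What does not stand is that these points close the gap. An open list and generic reporting standards do not pre-specify a study-defined endpoint. The SAE total is neither specific to infections nor certain to include every event in the 9.4.2 definition. Even the descriptive grouped summary that the protocol promises is not named in the readable SAP.

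**Conclusion.** The point holds as a gap between protocol and SAP. A safety endpoint that the protocol defines is not carried over, and the remaining rules either split infections by term or merge them into totals. The textual finding rests on no assumption beyond the SAP text that can be read.

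The size depends on assumed rates. For terms at about 2% to 5%, a given 40-participant arm reaches the Tier 2 threshold with probability 0.8% to 13.8%; at 10% or more, a comparison is likely. For serious infections alone the trial is small, and even a well-specified analysis will mostly give wide intervals. The gain lies in a pre-specified, complete count by arm with an honest interval, rather than in power to detect a difference. The SAP should be corrected before unblinding. The primary efficacy analysis is not affected.

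**What to change.** In SAP 3.4, add serious infections, using the Protocol 9.4.2 definition, as a grouped safety endpoint. In SAP 6.8.1, either name it in the first sentence as a binary safety endpoint, or make it Tier 1 and replace the sentence that rules Tier 1 out. If Tier 1 is chosen, the Safety Review Plan must be aligned as well. Specify participant counts by arm and the risk difference with exact 95% confidence interval for each dose against placebo, limited to Weeks 0-16 because the extension has no placebo arm. State how hospitalisation and parenteral antimicrobial use will be identified in the data, so that the group is fixed before unblinding.

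Two additions are optional. One is a pooled-dose comparison (120 against 40), which gains numbers but can dilute a signal confined to the higher doses. The other is a grouped count of confirmed herpetiform infections from the Section 8.2.6 specimens.

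The cost is one or two tables from data already collected, using a method already in 6.8.1. The downside is a few more unadjusted safety comparisons of low precision, which should be labelled as such.
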